25.0 Data Collection: (This section is required for all studies.)

25.1 Provide a general description of the types or categories of data that will be collected during the study (e.g., lab tests, procedure outcomes, length of stay, questionnaires, surveys). You will provide details on identifiable data and sensitive data below.

This study will be completely integrated into the Diabetes Data Dock at CMKC. Data will be collected and paired with the other wearable devices, such as pump and continuous glucose monitor readings.

The following data may be collected for this study: HbA1c values collected from EHR; device uploads, date of birth, age, gender, height, weight, race, ethnicity, address, phone number (parent, child, close friend), place of birth, primary language, parent age (mother & father), parent education (mother & father), parent occupation (mother & father), family income, parent marital status, medical history, (such as date of T1D diagnosis, T1D-related hospitalizations, treatment regimen, number of contacts and visits with clinic staff, insurance type, and blood glucose data, etc.) physical activity calendars, data from the actigraph, questionnaires and surveys as noted in Section 5.0, Study Design.

Demographic data: We will use a data collection form in REDCap^{33,34} to collect demographic data. We may use the Diabetes Data Dock/ electronic health record to verify or extend participant demographic data listed above (e.g., T1D diagnosis, history of T1D-related

complications, T1D regimen). For remote visits, we will share a web URL linking to the REDCap survey. Participants may complete Surveys on iPad for in person visit or at home via email or text using Twilio as noted in Section 10.0, Procedures.

HbA1c data: We will use routine T1D care POC HbA1c levels to at baseline and at post-treatment (~3 months post baseline).

CGM or SMBG data: Families will use their personal, prescribed CGM or standard blood glucose monitor (SMBG) throughout the study. Families will share CGM data with the study team using their personal, CM connected account. To facilitate data sharing, we will ask participants and parent/LAR of youth to please share a .CSV file version of these data. Study staff will save participant's CGM or SMBG in a secured study database using MS Excel or equivalent software. Data will be download automatically to the Diabetes Data Dock using API. This study database will reside in a secured CM approved location.

Garmin data and activity monitor: data will be downloaded and stored on the Diabetes Data Dock using API connection. Primary physical data will be gathered from the Garmin Connect platform. The anonymous participant Garmin data from the Garmin Connect platform will be loaded to a secure database through the Garmin Health API connection developed by Children's Mercy Research Informatics. The Garmin tracker will not collect personal information. Physical activity data will be pulled from the actigraph via the Actilife software and uploaded into the secure database. Also, the patient study record will be linked to the Garmin tracker and the actigraph. The interventionist team will be able to pull the data to Microsoft Azure database to evaluate. Coded clinical data will also be collected from EMR.

Insulin delivery data: Participants will use their personal, prescribed insulin delivery device throughout the study. Participants and parents/LARs of adolescents will share participants' insulin device data with the study team using their personal, CM connected account. To facilitate data sharing, we will ask families to please share a .CSV file version of these data. Study staff will save participant's insulin device data in a secured study database using MS Excel or equivalent software. This study database will reside in a secured CM approved location.

Questionnaire data: We will use REDCap to electronically collect any survey data, including participants' daily activity schedules. We will use a single REDCap database for all study participants. This REDCap data base will reside on a CM secured server.

Name/Initials	☐ Accessed only	⊠ Recorded
All elements of date (except year) directly related to an individual (e.g. date of birth, admission date, discharge date, date of death)	☐ Accessed only	⊠ Recorded

Medical record number	☐ Accessed only	⊠ Recorded
Account number	☐ Accessed only	□Recorded
Health plan identification number	☐ Accessed only	☐ Recorded
Social Security Number	☐ Accessed only	⊠ Recorded
Device identifiers and serial number	☐ Accessed only	☐ Recorded
Certificate/License number	☐ Accessed only	
Telephone number	☐ Accessed only	⊠ Recorded
Fax number	☐ Accessed only	⊠ Recorded
Email addresses	☐ Accessed only	⊠ Recorded
Web addresses (URLs); Internet IP addresses	☐ Accessed only	☐ Recorded
Street address, city, county, precinct, zip code or equivalent geographical codes	☐ Accessed only	⊠ Recorded
Full face photographic images and any comparable images	☐ Accessed only	☐ Recorded
Biometric identifiers, including finger and voice print	☐ Accessed only	☐ Recorded
Vehicle identifiers and serial numbers, including license plate number	☐ Accessed only	☐ Recorded
Any other unique identifying number, characteristic or code that may help identify individual participants including their initials (e.g. student or employee ID number)	☐ Accessed only	☐ Recorded
Elements of date, including year, for persons 90 years or older	☐ Accessed only	☐ Recorded
Other: Insurance type (public vs. private)	☐ Accessed only	⊠ Recorded

26.0 Adverse Events and Unanticipated Problems

26.1 Monitoring: *Describe your process for monitoring subjects and data to identify adverse events and other unanticipated problems.*

The only anticipated Adverse Event is potential Breach of Confidentiality. Please see Sections 9.0 (Screening and Recruitment Methods), 23.0 (Provisions to Protect the Privacy Interests of Subjects), 25.0 (Data Management), and 28.0 (Data and Specimen Management), of this protocol for procedures to prevent and/or reduce this risk.

26.2 Reporting: Confirm that you will be following Policy 5.11 Reportable Events of the CM Research Program Policies in regards to reporting adverse events and other unanticipated problems to the CM IRB. If you will be deviating from or expanding upon this policy, explain why the approved policy would not suffice for this study and the rationale for deviating/expanding.

Policy 5.11 Reportable Events will be followed.

27.0 Statistical Analysis

27.1 Describe the data analysis plan, including any statistical procedures or power analysis.

This is a pilot data collection in order to perform power calculations for a larger study.

AIM 1 and Hypotheses 1 and 2: Refer to Section 3.0, Objectives for explanation.

Data Analysis: We will use descriptive statistics to examine feasibility based on the percent of daily text messages exchanged between youth and the NUDGE bot. This will serve as our primary feasibility assessment. However, we will also consider feasibility based on other parameters including percent of days that youth wear the actigraph and the percent of daily PA schedules that participants complete. We will use multilevel analyses to determine whether the NUDGE intervention increased participants MVPA levels. In particular, we will examine the effect size of NUDGE and interpret at least a medium effect size as our threshold of initial treatment efficacy.

AIM 2 and Hypothesis 3: Refer to Section 3.0. Objectives for explanation.

Data Analyses: We will use multilevel analyses to determine whether the NUDGE intervention improved participants HbA1c levels. As explained above, we will focus on measuring the effect size for change in participant HbA1c for this hypothesis as well.

27.2 Describe how the sample size for the study was determined (e.g. formal sample size calculation, convenience sampling). To minimize the risks associated with a possible breach of confidentiality, appropriate sample size calculations limit the amount of patient data being recorded to just the amount necessary to answer the research question.

This is a pilot data collection in order to perform power calculations for a larger study.

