1.0 Study Summary 1.1 Synopsis

Study Title	Novel mHealth Physical Activity Intervention for Adolescents and Young Adults with Type 1 Diabetes (T1D)
Study Design	Non-randomized, longitudinal cohort study to pilot an intervention
Primary Objective	To evaluate feasibility and initial efficacy of a novel mHealth intervention to promote physical activity in youth and young adults with T1D
Secondary Objective(s)	To examine if increasing minutes of daily PA in youth and young adults with T1D promotes more optimal HbA1c levels.

Research Intervention(s)/ Investigational Agent(s)	Novel mHealth intervention (i.e., uses daily two-way text messaging) designed to promote physical activity in adolescents and young adults.
IND/IDE #	NA
Study Population	Patients 13.00 to 21.99 with T1D
Sample Size	250
Study Duration for Individual Participants	4.5 months (timeframe between standard of care visits)
Study Specific Abbreviations/F Definitions	T1D= Type 1 diabetes HbA1c= glycated hemoglobin PA= physical activity YA(s) = young adult(s) MVPA= moderate to vigorous physical activity NUDGE= Network Underwritten Dynamic Goals Exchange EMA= ecological momentary assessment

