4.0 Study Endpoints

4.1 *Describe the primary and secondary study endpoints.*

The primary endpoint is to increase daily PA in pediatric patients with T1D. The secondary endpoint is to improve HbA1c levels in pediatric patients with T1D.

Initial Efficacy Assessment. We will evaluate initial efficacy based on change in minutes of daily MVPA in adolescents from baseline to post-treatment, change in minutes of daily SB in adolescents from baseline to post-treatment, and change in HbA1c levels in adolescents from baseline to post-treatment.

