4.2 Describe the primary and secondary safety endpoints. **NA**

5.0 Study Design

5.1 Study Design: *Describe and explain the study design.*

We propose to pilot NUDGE in youth with T1D and look at treatment effects after at least 3 months. We anticipate the entire pilot study will last 12 months.

5.2 Schema: a schema is a representation of your study design in the form of an outline or a model. Including a schema is not a requirement but can be valuable tool in the presentation of your study to the IRB. Consider adding a diagram that provides a quick "snapshot" of the study.

Study Visit Procedures

5.3 *Table of Events*

	Consent	Visit 1 (Day	Day 25	Visit 2 (Day	Day 85	Visit 3 (Day	Daily	PRN (SOC)
	(Day -10 to	1 to 7)		30 to 37)		90 to 97)		
	-5)							
I/E Criteria	X							
E-Consent PAC	Х							
Baseline Survey	Χ							

Medical Chart	Χ							
Review for								
demographics								
Medical Records	Χ							X
– HbA1c								
Medical Records	Χ						X	
device uploads								
PA Calendar	Χ							
PA Goal Set	Χ						X	
Actiwatch	Χ		Х		X			
Shipment								
Actigraph	Χ		X		X			
Shipment								
Participant		X		X		X		
wears Aciwatch								
Participant		Х		Х		Х		
wears Actigraph								
Participant to co		Х		X		Х		
mplete								
EMA REDcap Sur								
vey (7 days,								
4x/day)								
Treatment						X		
Satisfaction								
Survey and Post								
Survey								

All questionnaires are outlined in Section 11.0.

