8.0 Local Number of Subjects

8.1 Indicate the total number of subjects or charts to be enrolled locally as well as the accrual goal. If the study includes multiple groups or cohorts, be sure to describe the number of subjects required for each cohort. If one of the groups includes a chart review, each chart is considered a subject and needs to be reflected in the numbers below.

Target sample size is one group of 50 participants.

	Group 1	Group 2	Totals
Accrual Goal:	50	NA	
The number of evaluable subjects/charts you are targeting for the required			

andraint for the		
endpoint for the		
study.		
This number		
typically is based		
on statistical input		
such as a power		
analysis.		
_		
Anticipated	70	
Anticipated	/0	
Enrolled/Consented:		
This is the		
number reported		
at Continuing		
Review.		
Estimated number		
of subjects/charts		
that you anticipate		
you will need to		
enroll in order to		
meet your accrual		
goal above.		
This can generally		
be calculated as		
accrual goal +		
number of		
anticipated screen		
failures + number		
of potential		
withdrawals/drop		
outs.		
A (1.70	250	
Anticipated Pre-	250	
	250	
Screened (if applicable):	250	
Screened (if applicable): Estimated number	250	
Screened (if applicable): Estimated number of subjects/charts	250	
Screened (if applicable): Estimated number of subjects/charts you anticipate you	250	
Screened (if applicable): Estimated number of subjects/charts you anticipate you will screen prior to	250	
Screened (if applicable): Estimated number of subjects/charts you anticipate you will screen prior to	250	
Screened (if applicable): Estimated number of subjects/charts you anticipate you will screen prior to obtaining	250	
Screened (if applicable): Estimated number of subjects/charts you anticipate you will screen prior to obtaining permission/assent/	250	
Screened (if applicable): Estimated number of subjects/charts you anticipate you will screen prior to obtaining permission/assent/consent.	250	
Screened (if applicable): Estimated number of subjects/charts you anticipate you will screen prior to obtaining permission/assent/consent. For example, if	250	
Screened (if applicable): Estimated number of subjects/charts you anticipate you will screen prior to obtaining permission/assent/consent. For example, if your study	250	

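### Section 27.1 credits the whole pre-post MVPA change to NUDGE, but in one uncontrolled group any net calendar change cannot be told apart from it

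*Combined protocol and SAP*

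**What the plan says.** The synopsis (Section 1.1) describes a "Non-randomized, longitudinal cohort study to pilot an intervention", and Section 8.1 adds: "Target sample size is one group of 50 participants". There is no control group.

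Section 4.1 defines efficacy through "change in minutes of daily MVPA in adolescents from baseline to post-treatment", alongside changes in sedentary behaviour and HbA1c. The Table of Events (5.3) places the wear weeks at Days 1-7, 30-37 and 90-97. Section 5.1 plans to "look at treatment effects after at least 3 months" and says: "We anticipate the entire pilot study will last 12 months". The synopsis gives 4.5 months of participation per person.

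On analysis, Section 27.1 says: "We will use multilevel analyses to determine whether the NUDGE intervention increased participants MVPA levels". It then speaks of the effect size of NUDGE and sets at least a medium effect as the threshold. HbA1c gets a parallel sentence with the same causal verb. No fixed effects or covariates are named for either model, and school session, season and calendar date appear nowhere as analysis terms. Sections 27.1 and 27.2 give the purpose as supplying power calculations for a larger study.

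**The concern.** Each participant's last wear week falls about 90 days, roughly a quarter of a year, after the first. Anything that shifts adolescents' activity over that interval, such as weather, daylight or a school break, enters the pre-post contrast in full. The Day 30-37 wave does not help: without a control group or a calendar term, three time points separate time from treatment no better than two.

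The wording of 27.1 nevertheless assigns the change to NUDGE and reads it against a pass mark. Two things are at stake. The pilot could report an efficacy signal, or the lack of one, that belongs partly to the calendar. And the same effect size is meant to feed the design of the next trial. The earlier NUDGE trial described in Section 3.3 had 20 controls beside its 20 treated adolescents; this study has none.

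**Working it through.** **The plan's own figure.** The target of 50 cannot be reproduced, because no alpha, power, SD or effect size is given for it. It is used below only as N.

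**Inputs from the documents.** One group, N = 50 (8.1). First and last wear weeks about 90 days apart (5.3). Total duration 12 months (5.1). Participation 4.5 months (1.1). Consent from Day -10 and last wear day 97 (5.3).

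**Assumptions, not in the documents.** A yearly sinusoidal MVPA cycle of amplitude A = 5-10 min/day; an SD of 15-25 min; medium read as d = 0.5; a summer break of 10-11 weeks; even entry within the window.

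**Entry window.** 12 - 4.5 = 7.5 months, about 228 days. Counting only to the last wear day, 365 - 97 - 10 = 258 days.

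**Worst-case seasonal shift.** For a quarter-year gap and even entry over a fraction f of the year, the largest mean shift is A x √2 x sin(πf)/(πf).

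| Entry window | f | Factor | Shift, A = 5 to 10 (min/day) | d, smallest to largest |
|---|---|---|---|---|
| 30 days | 0.082 | 1.40 | 7.0 to 14.0 | 7.0/25 = 0.28 to 14.0/15 = 0.93 |
| 60 days | 0.164 | 1.35 | 6.8 to 13.5 | 6.8/25 = 0.27 to 13.5/15 = 0.90 |
| 228 days | 0.625 | 0.665 | 3.3 to 6.7 | 3.3/25 = 0.13 to 6.7/15 = 0.44 |
| 258 days | 0.707 | 0.507 | 2.5 to 5.1 | 2.5/25 = 0.10 to 5.1/15 = 0.34 |
| 365 days | 1 | 0 | 0 | 0 |

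These are maxima over start dates, and the sign can go either way.

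**School break (1 June to 15 August assumed).** With entry over 228-258 days, the net share of participants moving into or out of the break is at most 0.29-0.33. A break effect of 0.5/0.33 = 1.5 to 0.5/0.29 = 1.7 SD would then be needed to reach 0.5 on its own. With entry bunched into 30-60 days the net share can reach 1.00, so a break effect of 0.5 SD is enough.

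**Consequence for the threshold.** Take no NUDGE effect, N = 50 and a calendar shift c in units of the SD of change. Then P(observed d ≥ 0.5) = 1 - Φ((0.5 - c)√50), and P(significant rise, two-sided 0.05) = 1 - Φ(1.96 - c√50).

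| c | P(d ≥ 0.5) | P(significant rise) |
|---|---|---|
| 0 | 0.0002 | 0.025 |
| 0.10 | 0.002 | 0.11 |
| 0.20 | 0.017 | 0.29 |
| 0.34 | 0.13 | 0.67 |
| 0.44 | 0.34 | 0.88 |

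The d values in the first table use a between-person SD. Since SD of change = SD x √(2(1 - r)), the two scales agree when the correlation r between waves is 0.5.

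**Consequence for planning (illustration).** If the true d were 0.40 and the calendar added 0.13, a trial planned at 0.53 would have (0.40/0.53)² = 57% of the participants it needs.

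**Precision cost of a calendar term.** This comes from the design matrix for 50 evenly spaced entries with person effects, as the ratio of the SE of the Day 90-97 contrast with the term to that without it.

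- Ten-week break indicator, 228-day window: 1.00-1.21 using first and last waves; up to about 1.15 using all three.
- Sine/cosine pair: 1.37-1.43 at 228 days; 1.17-1.19 at 258 days.
- Entry bunched into 30-60 days (three waves): the break term (1 June to 15 August) cannot be estimated for 28-43 of 73 start dates tried, and elsewhere the SE rises up to 4.5-fold. The sine/cosine pair inflates it at least 13-fold.

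**The case against.** The strongest reply is that this is a declared pilot of initial efficacy, that 27.1 names no model terms at all rather than excluding season, and that the size of any calendar effect comes from assumptions outside the documents. Even on those assumptions, the worst case with entry over 228-258 days stays below 0.5, and rolling entry cancels part of the shift. All of that stands, and it limits how strongly the point can be put. It does not remove the causal verb, the pass mark or the stated onward use of the effect size.

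Three practical objections also stand. School enrolment is not among the data listed in Sections 10.1 and 25.1, and participants may be up to 21.99 years old, so a break indicator would have to come from dates and would misclassify some young adults. The plan does not require staggered entry, and where entry is bunched and the bias is largest, a calendar term is least estimable. And each wave is a seven-day wear period, so complete weeks already balance weekdays and weekends; no weekday term is needed on this account.

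Finally, Hypotheses 2 and 3 (2.2) do not contain the wording of 27.1. Hypothesis 2 sets an effect-size threshold, and Hypothesis 3 links increased activity to better HbA1c. They need not be rewritten.

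**Conclusion.** The point holds in a limited form. Followed as written, 27.1 counts any net calendar change between baseline and Days 90-97 as NUDGE effect, in an unknown direction. Under the assumed cycle and SD, the worst case is about d = 0.10-0.44 for even entry over 228-258 days. It is near zero for even entry over a full year, and can exceed 0.5 if entry is bunched into one or two months.

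A reader might infer more than this, and the documents do not support it:

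- **That a spurious effect will be reported.** No seasonal or school effect size appears in the documents, and the shift may equally mask a benefit.
- **That entry cannot cover the year evenly.** The 12 months in 5.1 is an anticipated duration, and no entry pattern is laid down.
- **That the plan rejects calendar adjustment.** It is silent on all model terms.
- **That covariates would restore a causal reading.** Regression to the mean and reactivity to monitoring would remain. Goal setting is also scheduled from consent and daily (5.3), so the Day 1-7 baseline may itself not be free of the intervention.

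The correction to what the study can conclude does not depend on the assumed amplitude, SD or entry pattern.

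**What to change.** In Section 27.1:

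1. For both MVPA and HbA1c, replace the aim of determining whether NUDGE increased or improved the outcome with estimating the within-person change from baseline during NUDGE use. Call the effect size that of the pre-post change.
2. State that attributing the change to NUDGE, and using the effect size for planning, needs the later controlled study.
3. Adjust the daily MVPA model for device-recorded wear time. This does not address season; it guards against wear differing between waves, and wear is already measured for feasibility (10.1).
4. Report the distribution of entry dates. Where entry is spread enough to estimate it, add a sensitivity analysis with a date-based calendar term: a summer-break indicator defined by a stated date rule, or a season term. Note that a break indicator may misclassify participants aged 18-21 who are not in school.

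Hypotheses 2 and 3 need only be read in line with the revised text.

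The cost is analysis-plan wording, a softer claim and a wider interval in the sensitivity analysis: an SE 0-21% larger for a break term with staggered entry, about 40% larger for sine/cosine with a 228-day window, and much larger or not estimable if entry is bunched. No new data collection is needed.

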2.2 Hypotheses: *State the hypothesis to be tested.*

AIM 1: Test feasibility and initial efficacy of a novel mHealth intervention to promote PA in youth and YAs with T1D.

Hypothesis 1: Our application of a novel mHealth intervention to promote PA in youth and YAs with T1D will show feasibility based on ≥50% of daily text messages exchanged between youth and the intervention bot.

Hypothesis 2: Our application of a novel mHealth intervention to promote PA in youth and YAs with T1D will show initial efficacy based on the threshold of achieving at least a medium effect size for participant's daily PA.

AIM 2: Evaluate if increasing minutes of PA in youth and YAs with T1D promotes more optimal HbA1c levels.

Hypotheses 3: Youth and YAs with T1D who increase their daily PA based on our novel mHealth intervention will also show an improvement in their HbA1c levels.

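### Aim 2 and Hypothesis 3 ask whether raising physical activity improves HbA1c, but section 27.1 plans only an effect size for HbA1c change, which in one uncontrolled group cannot on its own support that claim

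*Combined protocol and SAP*

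**What the plan says.** The question is put three times, each time as a link between PA and HbA1c.

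- Section 1.1, secondary objective: "To examine if increasing minutes of daily PA in youth and young adults with T1D promotes more optimal HbA1c levels".
- Section 2.2, Aim 2: "Evaluate if increasing minutes of PA in youth and YAs with T1D promotes more optimal HbA1c levels".
- Section 2.2, Hypothesis 3, about participants "who increase their daily PA based on our novel mHealth intervention will also show an improvement in their HbA1c levels".

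The endpoint and the analysis are put differently.

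- Section 4.1: "The secondary endpoint is to improve HbA1c levels in pediatric patients with T1D". The same section lists HbA1c change and "change in minutes of daily MVPA in adolescents from baseline to post-treatment" as separate measures of initial efficacy.
- Section 27.1, Aim 2: "We will use multilevel analyses to determine whether the NUDGE intervention improved participants HbA1c levels", followed by "we will focus on measuring the effect size for change in participant HbA1c for this hypothesis as well".

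The study is non-randomized, and section 8.1 says "Target sample size is one group of 50 participants". Section 25.1 takes HbA1c from routine care at two points, baseline and about three months later. The section 5.3 table has three device wear weeks: Days 1-7, 30-37 and 90-97.

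**The concern.** The aim and hypothesis concern a relation between two changes. The analysis concerns the size of one of them. Section 27.1 names no PA predictor, no grouping by PA increase and no definition of an increase. Its cross-reference for Aim 2 points to Section 3.0, which is the Background; the aims are in Section 2.0, and neither section contains a model. Section 25.1 pairs the wearable-device data, but that is data handling.

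Two things are at stake. A favourable mean HbA1c change could be reported as support for Aim 2 when it may reflect something else. And if a PA-HbA1c estimate is made later, its exposure, time window, covariates and any cut-off for an increase would be chosen after the data are seen. A pilot meant to supply planning values for a larger study should fix these in advance.

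**Working it through.** The plan states no power, alpha, SD or correlation for Aim 2, so there is no figure to reproduce. The values below marked as assumed are illustrative.

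**1. What mean HbA1c change can show.** Let X be PA change and Y be HbA1c change, both in SD units, with correlation ρ and mean PA rise m. Write Y = c + ρX + error, where c is any change not related to PA (drift, treatment changes, season). Then mean Y = c + ρm. Assume m = 0.5.

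- With no drift (c = 0), mean Y is 0.00, -0.15 and -0.25 for ρ = 0, -0.3 and -0.5. Here the mean does move with the relation.
- With drift allowed, a mean of -0.25 arises from ρ = -0.5 and c = 0; from ρ = -0.3 and c = -0.25 + 0.15 = -0.10; or from ρ = 0 and c = -0.25.

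One observed mean cannot separate ρm from c. A control group would help to estimate c, and this design has none.

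**2. Hypothesis 3 read as a subgroup statement.** Take the group whose PA rose, X > 0. With m = 0.5 and a normal distribution, its expected share is Φ(0.5) = 0.69. Its mean X lies φ(0.5)/Φ(0.5) = 0.352/0.691 = 0.51 above m. In the remainder, mean X lies 0.352/0.309 = 1.14 below m. With the overall mean of Y held at -0.25:

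| ρ | PA rose | PA did not rise |
|---|---|---|
| 0 | -0.25 | -0.25 |
| -0.3 | -0.25 - 0.3 × 0.51 = -0.40 | -0.25 + 0.3 × 1.14 = 0.09 |
| -0.5 | -0.25 - 0.5 × 0.51 = -0.50 | -0.25 + 0.5 × 1.14 = 0.32 |

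At ρ = 0 those whose PA rose still improve by 0.25 SD. Improvement in that subgroup alone therefore does not show a relation; a contrast or a slope is needed.

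**3. Precision of a PA-HbA1c analysis.** Inputs: n = 50 from section 8.1, assumed to be complete pairs (the 250 in the synopsis appears in 8.1 as the number pre-screened); k covariates; two-sided 5%; 80% power. Detectable r = tanh[(1.96 + 0.84)/√(n - k - 3)].

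- n = 50, k = 0: tanh(2.80/√47) = 0.39.
- n = 50, k = 3: tanh(2.80/√44) = 0.40.
- n = 40, k = 3 (some pairs lost, assumed): tanh(2.80/√34) = 0.45.

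For an observed r of 0.30 with n = 50 and k = 0, the 95% interval is tanh(0.310 ± 1.96/√47) = 0.02 to 0.53. With k = 3, power at a true r of 0.30 is about 0.54 for 50 pairs and 0.44 for 40 pairs.

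**4. Timing of the exposure.** Section 10.1 treats HbA1c as reflecting the past 12 weeks, or 84 days.

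- A measurement at Day 90 (about three months, section 25.1) covers Days 6-90. It contains the Day 30-37 week and misses nearly all of Days 90-97.
- A measurement at 4.5 months (section 1.1; about Day 137) covers Days 53-137. It contains Days 90-97 but not Days 30-37.

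The Day 30-37 week lies wholly inside the window up to Day 30 + 84 = 114. The Day 90-97 week is complete only from Day 97. At the stated time of about three months, only the earlier week clearly precedes the outcome.

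**The case against.** Hypothesis 3 can be read at group level: Aim 1 asks whether MVPA rises, and Aim 2 asks whether HbA1c also improves. Section 4.1 lists the two changes side by side, and section 27.1 ties its HbA1c effect size to the hypothesis. This stands in part. On that reading the planned analysis largely addresses Hypothesis 3, though the secondary objective and Aim 2 still speak of PA promoting better HbA1c.

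Section 27.1 lists no model terms for either aim. A reader might infer that PA is excluded from the HbA1c model. The text does not say so; the term is unstated.

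A reader might also infer that mean HbA1c change carries no information about PA. That goes too far: step 1 shows that, without drift, the mean moves with the correlation. It stays constant across correlations only if the total fall is held fixed. The supportable statement is that the mean cannot separate the two sources.

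Finally, this is a secondary aim in a pilot, the analysis matches its stated endpoint, and a regression in 50 people would often miss a modest relation. All true. It favours rewording as a full remedy and cautious reporting of any regression. It does not make the present aim answerable by the present analysis.

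**Conclusion.** The mismatch is real and should be fixed, but it is limited. It lies between the secondary objective, Aim 2 and Hypothesis 3 on one side, and the section 4.1 endpoint and section 27.1 analysis on the other. Followed as written, the plan delivers the endpoint and partly serves a group-level Hypothesis 3, but cannot by itself support Aim 2.

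The size is shown by example: with an assumed mean PA rise of 0.5 SD, the same 0.25 SD fall in HbA1c fits any correlation from 0 to -0.5, depending on drift between -0.25 and 0. This rests on a linear relation; the subgroup figures also assume joint normality.

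A reader might conclude that the HbA1c endpoint is invalid or that the study cannot examine the PA-HbA1c relation. The documents do not support either. The endpoint is coherent, and MVPA and HbA1c are both already to be collected. Nor would adding the regression establish causation, since confounding would remain.

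**What to change.** Choose one of two changes.

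(a) Reword the secondary objective, Aim 2 and Hypothesis 3 to HbA1c change over the study, reported descriptively beside MVPA change. This costs only text, and gives up the PA-HbA1c question.

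(b) Add to section 27.1 an exploratory regression of post-treatment HbA1c on continuous within-person MVPA change, adjusted for baseline HbA1c, baseline MVPA and days between the two HbA1c measurements. Report the slope with its 95% confidence interval and the number of complete pairs, as an association and not a causal effect. Keep mean HbA1c change as the result for the section 4.1 endpoint. Four details need settling:

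- Name one MVPA device for both aims. Section 10.1 uses the actigraph and the Garmin; section 25.1 calls the Garmin data primary and also draws on the actigraph. These must be reconciled.
- Take the wear weeks from the section 5.3 table, because section 4.1 gives no days.
- Use an exposure week that precedes the HbA1c measurement: Days 30-37 minus Days 1-7 as primary, Days 90-97 minus Days 1-7 as sensitivity. The sensitivity analysis matters most where HbA1c is measured late.
- State that Days 1-7 may not be fully pre-intervention, since the section 5.3 table marks goal setting at consent and daily.

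Option (b) costs a few sentences and one model on data already planned, with no new visits. Its drawbacks are low precision and residual confounding, so the result should be read from the interval and not from a test.
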